Safety assessments	
The National Cancer Institute Common Terminology Criteria for Adverse Events (NCI CTCAE; Version 4.03 - www.hrc.govt.nz/sites/default/files/CTCAE%20manual%20-%20DMCC.pdf) will be used for grading toxicities. Safety assessments will include adverse events (AEs), serious adverse events (SAEs), physical examinations (PEs), vital sign measurements, clinical safety laboratory evaluations (hematology, serum chemistry, and urinalysis), ECOG scores, and ECGs.
 
The AE reporting period for a subject enrolled in the study begins when the subject provides informed consent and is continued through 30 days after the last dose of study drug or until start of new treatment. All AEs that occur in enrolled subjects during the AE reporting period specified in the protocol must be recorded, regardless of the relationship of the AE to study drug. Any known untoward event that occurs beyond the AE reporting period that the investigator assesses as possibly related to tesevatinib should be reported to Kadmon.
 
Vital sign measurements, including sitting blood pressure, pulse rate, respiratory rate, and temperature will be monitored throughout the study.
 
If \geq Grade 3 CTCAE AEs occur that are determined to be at least possibly related to study drug (with the exception of asymptomatic Grade 3 elevations of amylase or lipase, Grade 3 elevation of alkaline phosphatase in a subject known to have bone metastases, Grade 3 elevation of glucose in a subject receiving systemic corticosteroids, Grade 3 creatine phosphokinase [CPK] elevation in the absence of muscle symptoms, or Grade 3 sodium values \geq 126 mmol/L in a subject with diarrhea), tesevatinib will be withheld until all drug-related toxicities have resolved to \leq Grade 1.
 
If the QTc(F) interval increases to the level of \geq 500 msec study drug should be withheld and appropriate investigations undertaken.

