11.1.3.4 Response to QTc(F) Interval Prolongation

The following guidelines should be used in the management of QTc(F) prolongation. Subjects will have ECGs performed at times designated by the protocol.

If the QTc(F) interval increases to an absolute value of ≥ 60 msec above Cycle 1 Day 1 (predose on Day 1) but < 500 msec and the subject is asymptomatic (does not have palpitations, dizziness, syncope, orthostatic hypotension, or a significant ventricular arrhythmia on ECG), the following actions should be taken:

- Re-check and confirm concomitant medications for any medications that may be contributing to QTc(F) prolongation. Consult medical monitor for discontinuation of any medication found;
- Check electrolytes, especially magnesium and potassium; correct abnormalities as clinically indicated;
- Obtain blood sample (plasma) for PK analysis.

If the QTc(F) interval increases to an absolute value of ≥ 500 msec at any evaluation and if the subject is asymptomatic (does not have palpitations, dizziness, syncope, orthostatic hypotension, or a significant ventricular arrhythmia on ECG), then the following actions should be taken:

- Consult with medical monitor;
- Hold study drug;
- Re-check and confirm concomitant medications for any medications that may be contributing to QTc(F) prolongation. Consult medical monitor for discontinuation of any medication found;
- Check electrolytes, especially magnesium and potassium; correct abnormalities as clinically indicated;
- Obtain blood sample (plasma) for PK analysis;
- Contact medical monitor to discuss appropriate management;
- **QTc(F)**: When QTc(F) is within 30 msec of Cycle 1 Day 1 or ≤ 470 msec (whichever is lower), then study drug may be restarted with one dose level reduction;
- Following dose reduction and resumption of study drug treatment, ECGs must be repeated weekly for 2 weeks, then on Day 1 of each cycle per protocol following restart of study drug;
- Study drug may be restarted at the pre-event dose level if QTc(F) values of ≥ 500 msec are not confirmed by the central lab and if there is no evidence of drug-related abnormal ECG findings. This may be done as soon as the data are confirmed.

If the QTc(F) interval increases to an absolute value of ≥ 500 msec at any evaluation, and if the subject is or has recently been symptomatic (has palpitations, dizziness, syncope, orthostatic hypotension, a significant ventricular arrhythmia on ECG), then the following actions should be taken:

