Drugs associated with QT interval prolongation should be avoided in subjects receiving study drug unless deemed clinically necessary. Should a subject develop a condition for which a medication known to affect QT interval is indicated, consideration should be given to the additive risk of QT interval prolongation versus the potential benefit of treatment with the required medication and/or study drug. Contact the medical monitor prior to the administration of the concomitant medication.

During long-term follow-up, subjects who require short-term (2 to 3 weeks, not to exceed 21 days) treatment with a concomitant medication associated with QT interval prolongation while receiving study drug should have the study drug withheld until the concomitant treatment course is complete. The decision about whether the subject can continue on trial following this interruption will be determined by the medical monitor.

During long-term follow-up, subjects who require chronic treatment with a concomitant medication associated with QT interval prolongation while receiving study drug should be monitored as follows:

- Three ECGs should be obtained prior to start of the concomitant medication. These ECGs should be obtained within a total span of 30 minutes with an interval of approximately 1–2 minutes between recordings;

- If the average QTc(F) interval from these 3 ECGs is > 60 msec above the average Cycle 1 Day 1 (Day 1 predose) value or is ≥ 500 msec, study drug may be discontinued or dose reduced after discussion with the medical monitor;
- If both of the above criteria are not met (i.e., the average QTc[F] interval is no more than 60 msec above Cycle 1 Day 1 and is < 500 msec), ECGs should be obtained daily for the first 3 days of treatment with the concomitant medication;
- Additionally, an ECG should be obtained weekly for 2 weeks, then every 2 weeks for 1 month and monthly thereafter until the concomitant medication is no longer required or study drug is discontinued.

QTc(F) interval prolongation should be managed as noted in Section 11.1.3.3.

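### Protocol Section 12.3.1 ties its QT co-medication rules to the off-drug follow-up period and, read as intended, omits the hold that Section 11.1.3.4 requires at a QTcF of 500 msec or more

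*Protocol*

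**What the plan says.** **Period.** Section 12.3.1 has two operative paragraphs on QT-prolonging co-medication. The chronic-use paragraph begins "During long-term follow-up, subjects who require chronic treatment with a concomitant medication associated with QT interval prolongation while receiving study drug". The short-course paragraph (up to 21 days) opens with the same period and says that such subjects "should have the study drug withheld until the concomitant treatment course is complete". Elsewhere, long-term follow-up begins after withdrawal from active treatment and consists of a telephone call every 8 weeks (synopsis, Long-Term Follow-Up; Section 9.2.12). The long-term follow-up column of Tables 4-1 and 4-2 shows phone contact only, with no tesevatinib and no ECG.

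**Action at the limits.** For chronic use, three ECGs are taken before the co-medication starts. If their average is more than 60 msec above Cycle 1 Day 1, or is 500 msec or more, "study drug may be discontinued or dose reduced after discussion with the medical monitor".

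**General rule.** Section 11.1.3.4 applies when QTcF "increases to an absolute value of ≥ 500 msec at any evaluation and if the subject is asymptomatic". The instruction is "Hold study drug". Restart depends on recovery to within 30 msec of Cycle 1 Day 1 or to 470 msec ("whichever is lower), then study drug may be restarted with one dose level reduction"). Study drug may resume at the previous dose if the central laboratory does not confirm the value. At the same threshold the synopsis says "study drug should be withheld and appropriate investigations undertaken".

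**Pointers.** Section 12.3.1 closes by sending QTcF management to Section 11.1.3.3. Section 9.1.8 sends the reader to the same number for guidelines.

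**The concern.** The period is wrong for the people the rules describe. A subject in long-term follow-up takes no study drug, so there is nothing to hold or reduce and no visit at which to record an ECG.

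If the period is read as a slip and the rules are applied during treatment, a second problem appears. For one QTcF of 500 msec or more, the site finds a hold until recovery in one section and a choice of stopping or reducing the dose in another.

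What is at stake is the safe handling of an uncommon but risky combination. Section 5.1.2 reports centrally confirmed QTcF above 500 msec in 2 of 41 subjects at this study's dose of 300 mg daily. Section 5.2.1 reports that QTcF prolongation increased with plasma concentration, and Section 11.1.3.3 lists concurrent use of several QT-prolonging drugs among the risk factors for arrhythmia. The section written for that combination should give one instruction.

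**Working it through.** There is no planned figure to reproduce. The check sets the texts side by side.

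**1. Literal reading.** The rules apply in long-term follow-up, and long-term follow-up is off drug, so neither rule reaches a treated subject. The stated short-course hold and the fixed ECG calendar are lost. These remain:
- the 500 msec hold in Section 11.1.3.4;
- the routine ECGs in Section 9.1.8;
- contact with the medical monitor before the co-medication is given (Section 12.3.1, paragraph before the two rules);
- the investigator's discretionary hold of up to 28 days (Section 11.1.3), which is long enough for a 21-day course;
- close QTcF monitoring without a stated frequency (Appendix E).

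**2. Intended reading, asymptomatic subject at 500 msec or more.**

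| | Section 12.3.1, chronic use | Section 11.1.3.4 |
|---|---|---|
| Trigger | Average of three ECGs before the co-medication | Any evaluation |
| Action | Discontinue or reduce, after discussion | Consult the medical monitor and hold |
| Recovery level | None stated | Lower of Cycle 1 Day 1 + 30 msec and 470 msec |
| Resumption | Not addressed | One level lower; previous dose if not centrally confirmed |

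The restart level is min(Cycle 1 Day 1 + 30, 470), so it never exceeds 470 msec. As an illustration, assume a Cycle 1 Day 1 value of 430 msec and an average of 505 msec. Section 11.1.3.4 holds drug until QTcF is at or below min(460, 470) = 460 msec. The Section 12.3.1 bullet, taken alone, allows a reduced dose after discussion while QTcF is still 505 msec.

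**3. Symptomatic subject at 500 msec or more.** Section 11.1.3.4 calls for hospitalization and no further dosing, with a discussed exception for objective tumor response. The Section 12.3.1 bullet does not separate symptomatic from asymptomatic subjects.

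**4. Below 500 msec.** For a rise of 60 msec or more that stays below 500 msec without symptoms, Section 11.1.3.4 asks for a medication check, electrolytes and a PK sample, with no hold. The discontinue-or-reduce option does not contradict that. The difference is confined to 500 msec or more.

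**5. Pointers.** Section 11.1.3.3 gives precautions and symptom monitoring. It contains no hold rule and no restart rule; those are in Section 11.1.3.4.

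**6. ECGs (secondary).** On the intended reading, the three daily ECGs at the start of the co-medication are assigned only to subjects below both limits. The weekly and later ECGs carry no QTcF condition. Until those begin, a subject over a limit has the further monitoring that Section 9.1.8 requires above the same two limits, and the close monitoring in Appendix E. Neither has a stated frequency. After a dose-reduced restart, Section 11.1.3.4 adds: "Following dose reduction and resumption of study drug treatment, ECGs must be repeated weekly for 2 weeks".

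**The case against.** The strongest reply is that the sections can be read together. Section 12.3.1 ends by deferring to the QT management text. The number it gives is evidently one subsection off, since Section 9.1.8 uses the same number for guidelines and the guidelines follow immediately in Section 11.1.3.4. With that correction, Section 12.3.1 imports the hold. Its bullet can then be taken to name eventual outcomes, no restart or a lower dose, which are the usual results of the hold rule. Section 9.1.8 uses similar outcome wording at 500 msec or more, where it says the subject may leave the trial. The hold also applies at any evaluation, and the three ECGs before the co-medication are an evaluation.

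Much of this stands. A reader might infer that the protocol gives no guide to which rule prevails, or that it directs sites to keep dosing above 500 msec. Neither is supported: the deference is there, though misnumbered, and the general hold is never withdrawn. What the reply does not remove is the bullet itself. Even with the pointer corrected, it states a different action from a hold at the same reading and gives no recovery level.

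A reader might also count fixed ECGs over the first 28 days of co-medication:
- below both limits: days 1, 2, 3, 7, 14 and 28, which is 6, or days 1, 2, 3, 10 and 17, which is 5, if the weekly count starts after the third daily ECG;
- over a limit: days 7, 14 and 28, which is 3.

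This counts only the Section 12.3.1 calendar. It leaves out the monitoring in Section 9.1.8 and Appendix E, and it assumes that the subject stays on study drug. It does not demonstrate an ECG deficit.

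Nor does the distance of at least 500 − 470 = 30 msec between the trigger and the restart level measure risk. A hold-until-recovery rule has such a gap by design.

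**Conclusion.** The point holds as a wording inconsistency in operative safety text. Two parts are firm: the period named in Section 12.3.1 excludes every treated subject, and on the intended reading its chronic-use bullet omits the hold that Section 11.1.3.4 and the synopsis require at 500 msec or more. The misnumbered pointer leaves the reader to work out the link. The daily-ECG condition is a secondary observation.

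The practical size is small. These drugs are barred at entry (Sections 8.3, 8.5 and 8.7) and prohibited on study (synopsis; Section 12). A careful reader would probably hold. Sample size, error rates and efficacy results are untouched. The documents do not say how many subjects would need such a drug, so no risk is estimated. The conclusion on the hold assumes that Section 12.3.1 was meant for subjects on treatment, which its reference to receiving study drug supports. It should be fixed because the correction is cheap and the subjects concerned carry added QT risk.

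**What to change.** - In both operative paragraphs of Section 12.3.1, change the opening period to *During study treatment*.
- State that Section 11.1.3.4 governs at an average QTcF of 500 msec or more: for an asymptomatic subject, the hold and restart steps; for a symptomatic subject, the separate steps given there.
- Keep the discontinue-or-reduce option for a rise of more than 60 msec above Cycle 1 Day 1 with QTcF below 500 msec.
- Change the cross-reference from Section 11.1.3.3 to Section 11.1.3.4 in Sections 12.3.1 and 9.1.8.
- Optionally, assign the three daily ECGs to every subject who takes study drug together with a chronic QT-prolonging drug.

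The cost is protocol wording, since the hold, recovery level and ECG schedule already exist. The optional step adds at most three ECGs for a subject over either limit who continues on both drugs.

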13 PHARMACOKINETICS AND PHARMACODYNAMICS

13.1 Plasma and CSF Pharmacokinetics

For subjects with LM (Cohort B), PK samples will be drawn to evaluate tesevatinib pharmacokinetics. A plasma sample for tesevatinib PK analysis will be obtained at predose of tesevatinib on Cycle 1 Day 14 and at predose of tesevatinib on Cycle 3 Day 1. A plasma sample also will be obtained on Cycle 1 Day 14 and on Cycle 3 Day 1, within 4–8 hours after tesevatinib administration of the tesevatinib dose that day (i.e., at approximately the same time as the CSF PK sample is obtained).

For subjects with LM (Cohort B), CSF PK samples will be obtained on Cycle 1 Day 14 and on Cycle 3 Day 1, within approximately 4–8 hours after tesevatinib administration of the tesevatinib dose that day.

For all cohorts, additional samples for the preparation of plasma will be collected for tesevatinib analyses if the QTc(F) interval increases to the level of ≥ 500 msec (sample to be drawn as soon as possible after ECG performed).

13.2 CSF Pharmacodynamics

For subjects with LM (Cohort B), NSCLC cells in the CSF will be evaluated by both standard cytology and by a central rare cell detection methodology at Screening, on Day 14 of Cycle 1, and on Day 1 of Cycle 3. Samples will be evaluated for EGFR mutations (both the EGFR mutation or mutations known to be present in the tumor of a particular subject by prior investigation as well as for the T790M mutation and other EGFR mutations) and for EGFR copy number.

14 EFFICACY

In addition to bone scan at screening, CT scans of the thorax and abdomen will be performed at screening, after Cycle 2, and then every two cycles thereafter until disease progression.

Radiological disease assessments by brain MRI will be performed at screening, at C2D1, at C3D1, and then every two cycles until disease progression. Response for peripheral disease and for BM will be evaluated according to RECIST, Version 1.1. Response will be recorded separately for non-CNS disease, for BM, and for LM. All CT and MRI scans will be collected for central review. All clinical decisions during the study will be based on local site radiology assessments, which will also be used for the primary efficacy analysis.

For subjects with BM (Cohort A and Cohort C) efficacy will be evaluated by RECIST 1.1 criteria separately for non-CNS tumor lesions and for BMs at Screening, at Cycle 2 Day 1 (for BM), at Cycle 3, and then every 2 cycles (approximately 8 weeks) thereafter until disease progression.

For subjects with LM (Cohort B), symptoms attributed to leptomeningeal disease will be evaluated at screening, Cycle 1 Day 1, at Cycle 1 Day 14, at Cycle 2 Day 1, at Cycle 3, and then every 2 cycles (approximately 8 weeks) thereafter until disease progression.

The response efficacy endpoints will be evaluated separately for peripheral disease, for BM, and for LM, and a summary response will also be derived (See Table 14-1). For LM, if positive CSF cytology and MRI diagnostic findings were both present at screening, complete response (CR) requires the absence of LM by both modalities. For LM, CR also requires the complete resolution of symptoms and signs attributed to LM. Best overall response, duration of response, and duration of stable disease will be reported, based on the examples in Table 14-1. The median PFS, rate of CNS non-progression at 3 and 6 months, non-CNS time to progression, CNS TTP, and median OS also will be assessed.

Subjects with limited CNS or extra-CNS disease progression (oligoprogressive disease) may receive local ablative therapy (radiation therapy or surgery) and then be continued on tesevatinib. This practice is consistent with data indicating that some patients with NSCLC on TKI therapy who have oligoprogressive disease appear to have significant periods of additional disease control with this approach.¹⁹ Any such patients will be considered to have disease progression for analyses of PFS and for analyses of progression in the relevant (CNS or extra-CNS) compartment at the time of detection of oligoprogressive disease.

Subjects with scans that are on the “borderline” of disease progression (e.g. 21% increase in sum of target lesion diameters or equivocal findings on CSF cytology or MRI) but for whom the investigator determines a clinical benefit may occur in the study. These subjects will be allowed to continue in the study after discussion with the medical monitor. If improvement is documented at the next subsequent staging time point (e.g. 17% increase in sum of target lesion diameters or stable CNS symptoms), the subject will continue on study. If worsening is documented (e.g. 30% increase in sum of target lesion diameters or worsening of CNS symptoms), the subject should be discontinued from the study, and the progression date should be the original date on which “borderline” disease progression was first documented. If stable, then they will be followed until improvement or worsening occurs.

Table 14-1: Summary Response Examples

Peripheral Tumor ¹		Brain Metastases ¹		Leptomeningeal Metastases	Summary Response ³
Measurable	Non-measurable	Measurable	Non-Measurable		
CR	CR	CR ²	CR ²	CR ²	CR, peripheral, BM and LM
Non-CR, non-PD	Non-CR, non-PD	PR ²	None	Non-CR, non-PD	PR, BM only
Non-CR, non-PD	Non-CR, non-PD	CR ²	CR ²	Non-CR, non-PD	CR, BM only
Non-CR, non-PD	Non-CR, non-PD	Non-CR, non-PD	Non-CR, non-PD	CR ²	CR, LM only
Non-CR, non-PD	Non-CR, non-PD	Non-CR, non-PD	Non-CR, non-PD	None	CR, LM only
Non-CR, non-PD	Non-CR, non-PD	CR ²	None	CR ²	CR, BM and LM only
Non-CR, non-PD	Non-CR, non-PD	Non-CR, non-PD	Non-CR, non-PD	Non-CR, non-PD	SD

BM = bone metastases; CR = complete response; LM = leptomeningeal metastases; PD = progressive disease; PR = progressive response; SD = stable disease

- Using RECIST 1.1 criteria
- Diagnosis of BM CR or PR, or LM CR, requires that steroids be at or lower than dose of steroids at Cycle 1 Day 1 (if subject is receiving steroids)
- All summary response examples assume that no new lesions are present. A new peripheral tumor or brain metastasis, or symptom progression of LM will lead to a summary response of PD in that category.

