
	
LM on MRI), or non-PR, non-PD (continued presence of evidence of LM on MRI). PD for LM will not be defined by MRI.
 
The response efficacy endpoints will be evaluated separately for peripheral disease, for BM, and for LM, and a summary response will also be derived (See Table 14-1). For LM, if positive CSF cytology and MRI diagnostic findings were both present at screening, CR requires the absence of LM by both modalities. Best overall response, duration of response, and duration of stable disease will be reported, based on the examples in Table 14-1. PFS, rate of CNS non-progression at 3 and 6 months, non-CNS TTP, and CNS TTP, and OS also will be assessed.
 
Subjects with limited CNS or extra-CNS disease progression (oligoprogressive disease) may receive local ablative therapy (radiation therapy or surgery) and then be continued on tesevatinib. This practice is consistent with data indicating that some patients with NSCLC on TKI therapy who have oligoprogressive disease appear to have significant periods of additional disease control with this approach.¹⁶ Any such patients will be considered to have disease progression for analyses of PFS and for analyses of progression in the relevant (CNS or extra-CNS) compartment at the time of detection of oligoprogressive disease.
 
Subjects with scans that are on the “borderline” of disease progression (e.g. 21% increase in sum of target lesion diameters or equivocal findings on CSF cytology or MRI) but for whom the investigator determines a clinical benefit may occur in the study. These subjects will be allowed to continue in the study after discussion with the medical monitor. If improvement is documented at the next subsequent staging time point (e.g. 17% increase in sum of target lesion diameters or stable CNS symptoms), the subject will continue on study. If worsening is documented (e.g. 30% increase in sum of target lesion diameters or worsening of CNS symptoms), the subject should be discontinued from the study, and the progression date should be the original date on which “borderline” disease progression was first documented. If stable, then they will be followed until improvement or worsening occurs.

Quality of Life	
QOL will be evaluated via the EORTC QLQ-C30 and EORTC QLQ-BN20 questionnaires administered at Screening, on Day 1 of Cycle 3, and on Day 1 of odd-numbered cycles thereafter.

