with some degree of effectiveness.^{2,8,9} However, response rates are low and the time to disease progression is generally short with this treatment as well.

Diagnosis of BM is generally obtained by magnetic resonance imaging (MRI) of the brain. The diagnosis of LM is more complex. Diagnosis of LM is most definitive when cytologic evaluation of CSF specimens detects malignant cells. However, single CSF analysis has a false negative rate of approximately 50%, and thus cytologic diagnosis of LM often requires several separate CSF samples.¹⁰ MRI findings (such as subarachnoid nodules, enhancement in basal cisterns, and enhancement/clumping of nerve roots) are diagnostic, but normal CNS imaging does not exclude a diagnosis of LM. Antibodies to EpCam, an epithelial cell adhesion molecule, have been utilized to identify rare tumor cells such as circulating tumor cells in the blood. The same approach to rare cell capture has been utilized in the analysis of tumor cells in CSF. In one study of patients with LM, cytology had a sensitivity of 67%, MRI had a sensitivity of 73%, and EpCam based identification of CSF tumor cells had a sensitivity of 100%.¹¹ Cell-free DNA is present in patients with activating EGFR mutations and BM, and can be utilized to evaluate the EGFR mutations that are present.¹² Evaluation of cell-free DNA in the CSF may provide a method independent of cytological analysis for evaluation of the course of patients with LM.

Approximately 50% of erlotinib-resistant, EGFR-mutant patients harbor a T790M EGFR mutation, which gefitinib, erlotinib, and afatinib do not inhibit.^{1,2} IC₅₀s for one cell line with the T790M EGFR mutation were 10.4 μM for gefitinib, 16.1 μM for erlotinib, and 0.9 μM for tesevatinib.¹³ Despite having an IC₅₀ against cells with the T790M EGFR mutation that is much lower than that for gefitinib or erlotinib, tesevatinib was not effective in treating NSCLC patients with the T790M EGFR mutation in the XL647-203 study.¹⁴ However, patients with BM and LM occurring while receiving erlotinib therapy have been documented to have a much lower frequency (10%) of T790M mutation in the CNS than is the case for patients with progression in non-CNS locations (38%).¹⁵ This presumably occurs because erlotinib and afatinib and gefitinib penetrate poorly into the CNS, and thus tumor cells in the CNS can grow in the presence of the low levels of TKI that are present.

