14.2 Cohort B – Leptomeningeal Metastases

For subjects with LM, symptoms attributed to leptomeningeal metastases will be evaluated at screening, Cycle 1 Day 1, Cycle 1 Day 14, Cycle 2 Day 1, Cycle 3 Day 1, and then every 2 cycles (approximately 8 weeks) thereafter until disease progression, as well as at the End of Drug Treatment visit. CTCAE v4.03

(www.hrc.govt.nz/sites/default/files/CTCAE%20manual%20-%20DMCC.pdf) will be utilized for the evaluation of symptoms and signs attributed to leptomeningeal metastases. Symptom improvement is defined as a decrease in 1 grade in at least one CTCAE v4.03 symptom or sign attributed to leptomeningeal metastases without worsening of other neurologic symptoms or signs attributed to leptomeningeal metastases. Symptom progression is defined as an increase of 1 grade in at least one CTCAE v4.03 symptom attributed to leptomeningeal metastases or the appearance of new symptoms or signs of LM. Symptoms or signs attributed to leptomeningeal metastases will be followed as one component of the efficacy evaluation for Cohort B.

For subjects with LM, NSCLC cells in the CSF will be evaluated during the study (screening, Day 14 of Cycle 1, and on Day 1 of Cycle 3) for malignant cells both by standard cytological analysis and by a rare cell detection methodology. CSF obtained at the same time points will be evaluated for protein and glucose levels. Response will be based on standard cytological analysis if cytology was positive at screening. Response categories will be CR (no malignant cells, which must be present on 2 consecutive CSF evaluations to support response of CR), and non-PR, non-PD (continued presence of malignant cells). PD will not be defined by CSF cytology.

For subjects with LM (Cohort B), CSF for isolation of cell-free DNA will be collected at screening, Day 14 of Cycle 1, and Day 1 of Cycle 3. Evaluation for EGFR mutations will be performed. Quantitation of EGFR mutations in cell-free DNA will be utilized for an exploratory efficacy analysis.

LM will also be evaluated by serial MRI of the brain. For patients with positive findings of LM on MRI at screening, response categories will be CR (no evidence of LM on MRI), or non-PR, non-PD (continued presence of evidence of LM on MRI). PD for LM will not be defined by MRI.

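### Leptomeningeal complete response is judged only on the modality positive at screening, so an MRI-only subject can be a complete responder despite malignant cells in a later CSF sample

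*Protocol*

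**What the plan says.** Cohort B subjects may enter on CSF cytology, MRI or both (Protocol Section 8.4, criterion 5). Section 14 then states that "if positive CSF cytology and MRI diagnostic findings were both present at screening, complete response (CR) requires the absence of LM by both modalities". The synopsis carries the same condition, ending "CR requires the absence of LM by both modalities".

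Section 14.2 makes the same restriction test by test. On CSF: "Response will be based on standard cytological analysis if cytology was positive at screening". The MRI text opens "For patients with positive findings of LM on MRI at screening, response categories will be CR (no evidence of LM on MRI" and closes with a category for persistent findings. Neither test can produce LM progression: "PD will not be defined by CSF cytology", and "PD for LM will not be defined by MRI".

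Footnote 3 to Table 14-1 first says that the examples presuppose no new lesions, and then: "A new peripheral tumor or brain metastasis, or symptom progression of LM will lead to a summary response of PD in that category".

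Three further conditions narrow LM CR:
- Section 14 requires LM symptoms and signs to have resolved completely. The synopsis does not repeat this.
- Footnote 2 to Table 14-1 requires a steroid dose no higher than on Cycle 1 Day 1.
- A cytological CR needs two consecutive clear CSF evaluations (Section 14.2).

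Every Cohort B subject is scheduled for CSF at screening, C1D14 and C3D1, and for brain MRI at screening, C2D1, C3D1 and every two cycles after that. The SAP contains no definition of LM CR.

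**The concern.** The both-modality requirement shows that the protocol means LM CR to be absence of LM. It applies that meaning only to subjects positive on both tests at screening. For everyone else the second test is repeated on treatment but has no role in the CR call.

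The protocol's own background makes this hard to defend. Section 5.3.1 says that a "single CSF analysis has a false negative rate of approximately 50" per cent, and that normal imaging does not exclude LM. A negative screening result is therefore weak grounds for disregarding a later positive on the same test.

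At stake are the LM response, the summary response, best overall response and duration of response in Cohort B. With 20 subjects, one changed call moves a rate by 1/20 = 5 percentage points.

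**Working it through.** **The plan's own figure.** The Cohort B sample size rests on a 20% rate of symptom improvement with N = 20. From the exact binomial, P(X ≥ 3) = 1 − Σ C(20,k)·0.2^k·0.8^(20−k) over k = 0 to 2, which is 0.794 (stated: about 80%). P(X ≥ 2) = 0.931 (stated: over 90%). Both agree, and neither depends on LM CR.

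**The rule applied to every pattern.** Take symptoms as resolved and steroids as not raised. There are three screening patterns with at least one positive test and four on-treatment results for each, so 12 combinations.

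| Screening CSF / MRI | On-treatment CSF / MRI | As written | If both must be clear in all |
|---|---|---|---|
| + / + | − / − | CR | CR |
| + / + | any positive | not CR | not CR |
| − / + | − / − | CR | CR |
| − / + | **+ / −** | **CR** | **not CR** |
| − / + | − / + or + / + | not CR | not CR |
| + / − | − / − | CR | CR |
| + / − | **− / +** | **CR if footnote 3 is not read to bar it** | **not CR** |
| + / − | + / − or + / + | not CR | not CR |

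Exactly two patterns differ.

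**Does another rule catch them?**
- Progression: Section 14.2 excludes LM progression by cytology and by MRI.
- Footnote 3: the events it names as progression are a new peripheral tumor, a new brain metastasis and LM symptom progression. Its assumption of no new lesions could be read to cover new LM on MRI. It does not reach malignant cells in CSF.
- Borderline progression (Section 14): equivocal CSF or MRI findings are listed there, but the rule governs staying on study and does not bar CR.
- Appendix A: its new-lesion rule is headed for non-CNS response.
- SAP: nothing on LM CR.

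So the CSF-conversion pattern is LM CR as written, and the MRI-conversion pattern is ambiguous.

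**How timing plays out in an MRI-only subject.** Suppose malignant cells appear at C1D14, and at C2D1 the MRI is clear and symptoms are gone: LM CR at C2D1. Suppose instead that C1D14 is clear, CR is called at C2D1 and cells appear at C3D1: the call stands, and the only event the LM rules name that would end it is symptom progression.

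**Share of subjects exposed.** Inputs from Section 5.3.1: cytology sensitivity c = 0.67, or 0.50 from the single-sample false-negative rate; MRI sensitivity m = 0.73. The overlap b between the tests is not given, so it is varied. Among subjects positive on at least one test, the share positive on one only is (c + m − 2b)/(c + m − b).

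| c | Overlap assumed | b | Share on one test | Of 20 |
|---|---|---|---|---|
| 0.67 | independent, b = c·m | 0.489 | 0.422/0.911 = 46% | 9.3 |
| 0.67 | maximum, b = c | 0.67 | 0.06/0.73 = 8% | 1.6 |
| 0.67 | minimum, b = c + m − 1 | 0.40 | 0.60/1.00 = 60% | 12.0 |
| 0.50 | independent | 0.365 | 0.500/0.865 = 58% | 11.6 |
| 0.50 | maximum | 0.50 | 0.23/0.73 = 32% | 6.3 |
| 0.50 | minimum | 0.23 | 0.77/1.00 = 77% | 15.4 |

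**The case against.** The best defence is that this is a design choice. Section 7.2 admits that no validated way of measuring LM response exists, and a subject cannot respond on a test that was never positive. That justifies giving no response credit on a screening-negative test. It does not justify ignoring a later positive on that test.

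Second, footnote 3 presupposes no new lesions, and new leptomeningeal enhancement is arguably one. This stands in part. A reader might infer that nothing blocks either pattern, but the text supports that only for CSF conversion; for MRI conversion it is unclear.

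Third, the existing conditions are strict. Full resolution of LM symptoms and signs, with no steroid increase, leaves only asymptomatic conversion of the other test. This stands and limits the number of cases.

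Fourth, the SAP reports cytology by visit (Listing 1.4.1) and MRI findings by visit (Table 1.4.2, Listing 1.4.2) for all treated Cohort B subjects, and plans no hypothesis test. Conversions would therefore be visible. They would still have to be settled case by case, after the fact, in an open-label study whose primary efficacy analysis uses local scan readings.

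Fifth, a reader might reason that two on-treatment CSFs would reveal persistent disease at least once in 1 − 0.50² = 75% to 1 − 0.33² = 89% of MRI-only subjects. The documents do not support this. It treats the two samples as independent and gives full sensitivity to people who were cytology-negative at screening and who, to reach CR, have a clear MRI and no LM symptoms. Sensitivity in that group is plausibly lower.

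**Conclusion.** The concern holds in a limited form. As written, an MRI-positive, cytology-negative subject can be LM CR with malignant cells in an on-treatment CSF. The reverse case is not clearly barred. Both are confined to subjects whose LM symptoms have fully resolved without a steroid increase. The synopsis, which omits symptom resolution, leaves a wider gap than Section 14.

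The exposed share is illustrative: about 46% under assumed independence (8% to 60% by overlap), or 58% with 50% single-CSF sensitivity (32% to 77%). A reader might take these as false-CR rates. They are not: they count subjects judged on one test, and the documents give no basis for saying how many would convert without symptoms.

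Nor is the Cohort B primary endpoint affected, since it is improvement in CTCAE symptoms and signs. SAP Table 1.1.1 does list ORR, CR and PR by cohort as primary efficacy, but it never says what CR means in Cohort B, so a link from this rule to that table is inference.

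The definition should be corrected before analysis. The defect does not undermine the trial's main result.

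**What to change.** Put one rule in Section 14, the synopsis and the SAP:

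> LM CR requires that the most recent CSF cytology and the most recent brain MRI at the CR assessment both show no LM, whatever the screening result, in addition to symptom and sign resolution, the steroid condition and, for subjects cytology-positive at screening, two consecutive negative CSF evaluations. After the last scheduled CSF (C3D1), the last available CSF result is used. If a later CSF or MRI is positive for LM, LM CR ends on that date for duration of response, without being classed as LM PD.

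This handles both timings above: a positive C1D14 CSF blocks a call at C2D1, and a positive C3D1 CSF ends a CR called at C2D1. Also reconcile the synopsis with Section 14 on symptom resolution.

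The cost is wording only. CSF and MRI are already scheduled in every Cohort B subject, so no procedure is added, and the LM progression definition is unchanged. The LM CR count may be slightly lower and LM CR duration slightly shorter. Because no CSF is scheduled after C3D1, a subject whose last CSF was positive could not become LM CR later unless a further CSF happened to be available and clear; the SAP should say so openly.
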